8.0 Study Endpoints*

We will examine within-person changes in blood levels of estradiol, testosterone, dehydroepiandrosterone sulfate (DHEAS), and sex hormone-binding globulin (SHBG) after three weeks of one serving of white wine daily compared to levels after three weeks of one serving of white grape juice daily.

At visits 1, 2, 3, and 4, the BIDMC Clinical Research Center (CRC) nurses will obtain a fasting blood sample. Within 72 hours, Quest Diagnostics will measure hepatic function, a complete blood count, and following visits 2 and 4, they will conduct a lipid panel. On our weekly phone check-ins, we will ask about recent health events such as unscheduled hospitalizations or any symptoms that have developed since the last meeting.

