11.0 Data Management* and Confidentiality

We will present descriptive statistics on the proportion of people screened who were eligible and ineligible, and the number randomized. We will describe the health characteristics and self-reported adherence of the completers and non-completers based on the available data.

We will construct linear mixed models to examine within-person changes in levels of estradiol, testosterone, DHEAS, and SHBG from grape juice to white wine, including a random subject intercept and fixed effects for treatment and sequence. We will assess the potential for a carryover effect by evaluating a cross-product term for treatment and sequence. We will use a logarithmic transformation for skewed distributions of the sex hormone levels.

We will use Markov Chain Monte Carlo (MCMC) multiple imputation. For each treatment arm, we will use the SAS “proc mi” procedure to generate 10 multiply imputed datasets that incorporate appropriate variability across the imputations. We will use the SAS “proc mianalyze” procedure to combine the results from the imputed data sets to properly reflect the uncertainty due to missing values.

Our primary analysis will use an intention-to-treat (ITT) approach, classifying participants according to their assigned treatment arms regardless of adherence to study protocol. In a sensitivity analysis, we will use a per-protocol approach in which a participant’s follow-up will be terminated at the time, if any, at which they cease to follow the protocol, and we will adjust for pre-randomization and post-randomization factors that may predict adherence.

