Our primary endpoint is free estradiol (estradiol divided by SHBG). We should have excellent power to assess effects of alcohol on DHEAS but reasonable power to detect effects on estrone sulfate, although, as a pilot study with an intentional goal of training and career development, power is but one dimension on which to evaluate the merits of the trial. We have used standard formulae to estimate the minimum detectable difference for 2-period crossover trials (http://hedwig.mgh.harvard.edu/sample_size/js/js_crossover_quant.html). Using the 4-week results of a similar crossover trial of alcohol on changes in estrone sulfate and DHEAS, and using the dosage of 15 gm/day that most closely approximates the dosage proposed in this application, we can estimate the proportional changes anticipated with varying degrees of power, as shown below at a two-sided 0.05 significance level. Based upon data presented in that trial, we estimate the SD of within-person differences to be 42% for estrone sulfate and 13% for DHEAS.

Power	Minimum Detectable Difference	
	Estrone sulfate (ng/dl)	DHEAS (ng/dl)
50%	19%	6%
80%	28%	9%
90%	32%	10%

For comparison, the increases in estrone sulfate in previous trials of alcohol were 15-21% in a trial of premenopausal women and 7-22% in a trial of postmenopausal women.

The comparable effects on DHEAS were 4-7% and 5-9%. Thus, we appear to have adequate power to detect effects of the expected size from previous crossover trials. Moreover, we have particularly strong power to exclude virtually all clinically significant increases (e.g., increases of 10% or larger) in DHEAS.

Our results would also provide all necessary information to power a more definitive trial of estrone and other estrogens.

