We will obtain laboratory results about the safety measures from the Quest eResults system and manually enter the data into the study database. We will retain paper copies of the reports and periodically conduct audits to compare the entered data with the paper copies to ensure that it was accurately entered in the study database.

The Brigham Research Assay Core (BRAC) will conduct specimen analyses for sex hormones. We will centrifuge the samples for sex hormone assays and freeze the serum in aliquots at -80°C. At the end of the study, we will bring the samples to the BRAC. They will use liquid chromatography–mass spectrometry to measure estradiol, estrone, and testosterone, and they will use chemiluminescence to measure sex hormone binding globulin (SHBG) and dehydroepiandrosterone sulfate (DHEAS). We will follow their sampling, storage, and transport procedures.

We will obtain laboratory results about the sex hormone measures from the Freezerworks database on the BRAC web portal system and manually enter the data into the study database. We will retain paper copies of the reports and periodically conduct audits to compare the entered data with the paper copies to ensure that it was accurately entered in the study database.

Only members of the research team, including the CRC nurses, will have access to the data and specimens. Quest Diagnostics will transmit results through their secure

eResults system with study-specific account access. We will download results and enter the data into our study-specific REDCap database.

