23.0 Local Number of Subjects

We will screen and enroll participants until we have 20 participants who have completed the ten weeks of the study.

BIDMC follows over 5,000 women with breast cancer who account for over 8,000 visits yearly, of whom over 3,500 are likely to be ER+ and hence potentially eligible for our trial.

We plan to contact as many as 100 participants to ensure that at least 20 women complete the study. This pilot study is funded by very limited project funds from

[name] K01 award and comprises 20 women – a small enough total to be readily completed at a single center.

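### The only estrogen power statement concerns estrone sulfate, which is never assayed; the primary endpoint, free estradiol, has no SD, expected effect or power, and the role of estrone is undefined

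*Combined protocol and SAP*

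**What the plan says.** The power paragraph in section 11.0 opens by naming free estradiol, defined as estradiol over SHBG, as the primary endpoint. It then turns to two other hormones. From an earlier crossover trial, "we estimate the SD of within-person differences to be 42% for estrone sulfate and 13% for DHEAS". The table gives minimum detectable differences at 50%, 80% and 90% power of 19%, 28% and 32% for estrone sulfate and 6%, 9% and 10% for DHEAS, "as shown below at a two-sided 0.05 significance level". The comparison figures for the estrogen are that "the increases in estrone sulfate in previous trials of alcohol were 15-21% in a trial of premenopausal women and 7-22% in a trial of postmenopausal" participants; for DHEAS they are 4-7% and 5-9%. The text calls power for estrone sulfate reasonable and concludes that power is adequate for effects of the size seen before. The paragraph ends: "Our results would also provide all necessary information to power a more definitive trial of estrone and other estrogens".

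The outcome lists read differently. Section 8.0: "We will examine within-person changes in blood levels of estradiol, testosterone, dehydroepiandrosterone sulfate (DHEAS), and sex hormone-binding globulin (SHBG", where the list ends. The models in section 11.0 are "to examine within-person changes in levels of estradiol, testosterone, DHEAS, and SHBG from grape juice to white wine". The later laboratory text in section 11.0 says that mass spectrometry will be used "to measure estradiol, estrone, and testosterone". The assessment table in section 9.0 schedules estradiol and estrone four times.

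**The concern.** The hypothesis in section 1.0 is that the increases normally expected after light drinking will not appear in women on an aromatase inhibitor. A finding of no increase is informative only if the trial could have shown, or its interval can exclude, an increase of a stated size in a hormone that it measures. For estrogens, the only stated size and SD belong to estrone sulfate. If that hormone is not assayed, a reader who relies on the power statement would give a null estrogen result more weight than the plan has justified.

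Two linked gaps make this matter more. The primary endpoint has no planning figures and is missing from the places where outcomes are listed. And the pilot promises planning data for a later estrone trial without specifying any estrone analysis, so a decision to analyse estrone could be made after the estradiol results are known.

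**Working it through.** **1. Where each analyte appears**

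| Place | Estradiol | Free estradiol (ratio) | Estrone | Estrone sulfate |
|---|---|---|---|---|
| Section 8.0, endpoints | yes | no | no | no |
| Section 9.0, tube list under Blood Samples | yes | not an assay | no | no |
| Section 9.0, assessment table | yes, 4 times | not an assay | yes, 4 times | no |
| Section 11.0, mixed models | yes | no | no | no |
| Section 11.0, power paragraph | only as a component of the primary endpoint | primary; no SD, effect or power | named for a future trial | SD, detectable differences, prior increases |
| Section 11.0, hormone assay methods | yes | not an assay | yes | no |

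Estrone sulfate occurs in the power paragraph and nowhere else. Estrone is in two assay descriptions and missing from a third. With 20 completers and four visits, the schedule implies 20 × 4 = 80 estrone results.

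**2. Reproducing the plan's table**

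Inputs: 20 completers (section 23.0: "We will screen and enroll participants until we have 20 participants who have completed the ten weeks of the study"), two-sided 0.05, SDs of 42% and 13%.

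Standard error = SD/√20: 42/4.472 = 9.39% for estrone sulfate and 13/4.472 = 2.91% for DHEAS. Solving the noncentral t power function with 18 degrees of freedom:

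| Power | Estrone sulfate: computed (plan) | DHEAS: computed (plan) |
|---|---|---|
| 50% | 19.45% (19%) | 6.02% (6%) |
| 80% | 27.82% (28%) | 8.61% (9%) |
| 90% | 32.21% (32%) | 9.97% (10%) |

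All six figures match after rounding. With 19 degrees of freedom the rounded values are the same.

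**3. Power at the increases the plan quotes**

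Noncentrality = increase / standard error, same test.

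| Estrone sulfate increase | Noncentrality | Power |
|---|---|---|
| 7% | 7/9.39 = 0.75 | 10% |
| 15% | 15/9.39 = 1.60 | 33% |
| 21% | 21/9.39 = 2.24 | 56% |
| 22% | 22/9.39 = 2.34 | 60% |

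The 80% detectable difference (28%) is larger than every quoted increase (maximum 22%). DHEAS is the only measured hormone with a stated SD; its power is 26%, 37%, 62% and 83% at increases of 4%, 5%, 7% and 9%.

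**4. Free estradiol**

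No power can be computed from the documents, because they give neither an SD nor an expected effect for free estradiol or estradiol. Treating the SD of within-person differences as an assumption and keeping 20 completers and 80% power:

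| Assumed SD | Detectable difference |
|---|---|
| 20% | 13% |
| 30% | 20% |
| 50% | 33% |
| 60% | 40% |

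**5. Why the ratio must be named in the model**

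On the log scale, log free estradiol = log estradiol − log SHBG. The two component models therefore give its point estimate by subtraction. The standard error of the difference also depends on the covariance of the two contrasts, which separate models do not supply. The confidence interval for the primary endpoint needs its own model.

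**The case against.** The best defence has four parts.

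First, a reader might infer that the estrogen part of the objective has no outcome at all. The documents do not support that. Estradiol is an endpoint, is modelled, is in all three assay descriptions and is scheduled at four visits; free estradiol is declared primary. Section 1.0 speaks of sex hormones in general and names neither estrone nor estrone sulfate. This part stands: what is missing is a numeric benchmark for a measured estrogen, not an estrogen outcome.

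Second, the estrone sulfate ranges are offered as a comparison in a sample-size discussion and do not define the hypothesis. That is so. But the same paragraph draws a general conclusion of adequate power from them, and never calls estrone sulfate a proxy for estradiol.

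Third, estrone does have a stated purpose, namely planning a later trial, and the scheduled assays could supply its within-person SD. That also stands, so it would be too strong to say that the estrone data have no purpose or that the planning information will not be delivered. The supportable point is that no estrone analysis is specified. Nor do the documents say that estrone would remain measurable where estradiol does not, so it cannot be presented as a ready fallback.

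Fourth, the plan openly describes a training pilot in which power is one consideration among several. This limits the consequences but does not make the power statement correct, and planning data are themselves a promised product of the pilot.

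**Conclusion.** The point holds in this form. The plan's favourable power language for estrogens rests on a hormone that no section plans to measure. Even for that hormone, the plan's own inputs give about 10% to 60% power across the 7% to 22% increases it quotes. The primary endpoint has no stated SD, expected effect or power and is absent as a ratio from the endpoint and model lists. Estrone's role is unsettled across sections 8.0, 9.0 and 11.0.

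There is no arithmetic error: the table reproduces. The mismatch does not bias the estradiol estimate or change the conduct of the trial; it affects what a null estrogen result can be said to show and what the pilot will report.

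The power figures assume 20 completers, the plan's SDs, and percentage differences treated as approximately normal. The range for free estradiol rests entirely on assumed SDs of 20% to 60%. That no estrone analysis is planned is read from its absence in the endpoint and model lists; the plan does not expressly exclude one.

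**What to change.** - **Section 11.0, power paragraph.** Remove the power claim for estrone sulfate, or label that column as a different analyte not measured in this trial. State that power for free estradiol is not established, or show detectable differences over an assumed SD range (about 13% to 40% at 80% power for SDs of 20% to 60%).
- **Sections 8.0 and 11.0, endpoints and models.** Name free estradiol as the primary outcome with its own model. Add estrone as a named secondary outcome, on the log scale, reported as a wine-to-juice ratio with a 95% confidence interval.
- **Section 9.0.** Reconcile the tube list with the assessment table and with the assay methods in section 11.0, so that estrone's status is the same in all three.
- **Pilot output.** Commit to reporting within-person SDs for free estradiol, estradiol and estrone, and limit the closing promise about a later trial to the hormones measured.

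The cost is wording and two further models. If estrone is assayed as the assessment table and laboratory text say, no new visits or assays are needed; the tube list must be settled before that is certain. The downside is one more secondary outcome and a less favourable power statement. Declaring estrone exploratory, or dropping its assay, would also resolve the inconsistency, but dropping it would mean withdrawing the promise of estrone planning data.

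### The claim of adequate power contradicts the protocol's own table: power at the expected effects is 11-60% for estrone sulfate and 26-83% for DHEAS, and neither is the primary endpoint

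*Combined protocol and SAP*

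**What the plan says.** The power paragraph in Section 11.0 begins by naming the primary endpoint: "Our primary endpoint is free estradiol (estradiol divided by SHBG". It then turns to two other hormones: "We should have excellent power to assess effects of alcohol on DHEAS but reasonable power to detect effects on estrone sulfate".

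The method is described as follows: "We have used standard formulae to estimate the minimum detectable difference for 2-period crossover trials". The inputs are a two-sided 0.05 level and SDs of within-person differences of 42% for estrone sulfate and 13% for DHEAS, taken from an earlier crossover trial of alcohol. The table gives minimum detectable differences at 50%, 80% and 90% power of 19%, 28% and 32% for estrone sulfate and 6%, 9% and 10% for DHEAS.

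Earlier trials' increases in estrone sulfate are quoted for comparison: "15-21% in a trial of premenopausal women and 7-22% in a trial of postmenopausal women". The matching DHEAS effects are 4-7% and 5-9%. From this the plan concludes: "Thus, we appear to have adequate power to detect effects of the expected size from previous crossover trials". A further sentence claims particularly strong power to exclude DHEAS increases of 10% or more.

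The assay description later in Section 11.0 says the laboratory will use mass spectrometry "to measure estradiol, estrone, and testosterone, and they will use chemiluminescence to measure sex hormone binding globulin (SHBG) and dehydroepiandrosterone sulfate (DHEAS". Section 8.0 defines the endpoints as "within-person changes in blood levels of estradiol, testosterone, dehydroepiandrosterone sulfate (DHEAS), and sex hormone-binding globulin (SHBG". Section 23.0 fixes the sample size: "We will screen and enroll participants until we have 20 participants who have completed the ten weeks of the study".

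**The concern.** The conclusion can be compared with the table by eye. The largest quoted estrone sulfate effect, 22%, is below the 28% needed for 80% power. For DHEAS, the whole premenopausal range (4-7%) is below the required 9%, and the postmenopausal range (5-9%) only touches it at its upper end. Even the 50% power row (19% and 6%) lies above much of each range.

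The calculation also does not address the outcome the trial is meant to judge. Free estradiol is primary, yet the documents give it no SD, expected effect, detectable difference or power. One of the two hormones that do have a calculation, estrone sulfate, is not scheduled to be measured.

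This matters because of the direction of the hypothesis. Section 1.0 predicts that the expected increases will not be observed in women on aromatase inhibitors, so a non-significant result is the predicted one. If readers are told that power was adequate, they may take that result as evidence of no effect when the trial could well have missed an effect of the size seen before. Section 1.0 also says women need this information to make decisions about alcohol during treatment.

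**Working it through.** **Inputs.** From Section 11.0: two-sided alpha 0.05; SD of within-person differences 42% (estrone sulfate) and 13% (DHEAS); expected effects 7-22% and 4-9%. From Section 23.0: n = 20 completers, so no dropout deduction is needed.

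**Step 1: reproduce the table.** For a two-period crossover, SE = SD/√n.

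- Estrone sulfate: 42/√20 = 9.39%
- DHEAS: 13/√20 = 2.91%

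Power for a true difference d comes from the noncentral t distribution with 18 degrees of freedom (20 women, two sequences) and noncentrality d/SE. Solving for d:

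| Power | Estrone sulfate, computed | Plan | DHEAS, computed | Plan |
|---|---|---|---|---|
| 50% | 19.4% | 19% | 6.0% | 6% |
| 80% | 27.8% | 28% | 8.6% | 9% |
| 90% | 32.2% | 32% | 10.0% | 10% |

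All six entries agree after rounding, so the inputs are being read as the plan intended. Treating the SDs as per-measurement values (multiplying by √2) gives 26.0/37.2/43.1% and 8.1/11.5/13.3%, which does not match.

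**Step 2: power at the expected effects, same inputs.**

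| Hormone | True effect | d/SE | Power |
|---|---|---|---|
| Estrone sulfate | 7% | 0.75 | 11% |
| | 15% | 1.60 | 33% |
| | 21% | 2.24 | 56% |
| | 22% | 2.34 | 60% |
| DHEAS | 4% | 1.38 | 26% |
| | 5% | 1.72 | 37% |
| | 7% | 2.41 | 62% |
| | 9% | 3.10 | 83% |

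**Step 3: sensitivity to the formula.** A normal approximation gives 11-65% and 28-87%. Expressing the effects as log ratios, again with the normal approximation, gives 11-56% and 27-84%. Back-solving the SE from each rounded table entry gives 10-62% and 24-84%. The conclusion is the same each time.

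**Step 4: sample size that 80% power would need.** By the normal approximation, n = ((1.96 + 0.8416) × SD/d)².

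- Estrone sulfate: 29 women at 22%, 62 at 15%, 283 at 7%
- DHEAS: 17 women at 9%, 28 at 7%, 54 at 5%, 83 at 4%

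**Step 5: what can be said for the primary endpoint.** Power for free estradiol cannot be computed, because no SD is given. Precision can be stated as a multiple of an assumed SD: the 95% half-width is t(0.975, 18)/√20 × SD = 2.101/4.472 × SD = 0.47 × SD. As an illustration only, borrow the plan's two SDs as log-scale values. An SD of 0.13 gives a half-width of 0.061 (a ratio of about 1.06), and an SD of 0.42 gives 0.197 (a ratio of about 1.22). The documents do not show where free estradiol under aromatase inhibition would fall.

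**Step 6: assay and outcome lists.**

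- Section 9.0, blood tubes: DHEAS, FSH, LH, SHBG, estradiol, testosterone, progesterone
- Section 9.0, assessment table: estradiol and estrone, SHBG, DHEAS, testosterone
- Section 11.0, assays: estradiol, estrone, testosterone, SHBG, DHEAS
- Section 8.0 endpoints and Section 11.0 mixed model: estradiol, testosterone, DHEAS, SHBG

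Estrone sulfate appears in none of them. Free estradiol is not named in Section 8.0 or among the mixed-model outcomes.

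**The case against.** The best defence is that nothing is hidden. The plan prints the SDs, the level, the detectable differences and the prior effects side by side, hedges its conclusion, and says that in a training pilot power is only one consideration. The sample size was set by budget, and correcting the sentence changes neither the number of women nor the analysis. That is a fair argument for accepting low power. It does not justify calling that power adequate.

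A second point has more substance. The sentence on excluding DHEAS increases of 10% or more fits the hypothesis better than a detection claim does, and it is supported if the true effect is zero: the probability is about 90%. It falls to about 50% if the true increase is 4% and to 37% if it is 5%. The sentence can stay with its assumption stated, but it concerns neither estrogens nor the primary endpoint.

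Third, estrone sulfate may have been meant only as planning data, since Section 8.0 does not list it as an endpoint. The plan does not call it a proxy, however, and it speaks of detecting effects on it. Fourth, both components of free estradiol are measured, so its omission is a gap in specification and no data are lost. Fifth, no rule in the plan says that non-significance confirms the hypothesis, so the risk of misreading is an inference from how the hypothesis is worded.

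Finally, intention-to-treat analysis with multiple imputation could bring the analysed number above 20. Even 30 women would give only about 79% power at the largest estrone sulfate effect, 22%.

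**Conclusion.** The concern holds. The table is right and the conclusion drawn from it is wrong. At n = 20, with the plan's own SDs and a two-sided 0.05 level, power over the quoted effects is 11-60% for estrone sulfate and 26-83% for DHEAS. An estrone sulfate effect of the size seen in earlier trials would therefore be missed 40-89% of the time. Power of 80% is reached only for DHEAS effects of about 9% or more. Neither hormone is the primary endpoint, and one is not assayed. For free estradiol the plan makes no statement of power or precision at all.

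The result assumes that the stated SDs apply to this trial, that 20 women contribute both periods, and that adequate means the conventional 80%. The plan sets no other threshold, and most of the computed values would be low by any usual standard.

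**What to change.** In Section 11.0:

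- Replace the statements that power is adequate, excellent or reasonable with the computed values: 11-60% for estrone sulfate effects of 7-22% and 26-83% for DHEAS effects of 4-9%. State that 80% power to detect an effect is reached only for DHEAS, at about 9% or more.
- Keep the sentence on excluding a DHEAS increase of 10% or more, qualified as holding (about 90%) when the true effect is zero.
- Drop estrone sulfate as the powered outcome.
- For log free estradiol, give the detectable difference or the expected 95% half-width (0.47 × SD of the within-woman difference at n = 20) over a stated range of assumed SDs.
- Say that a non-significant result will be interpreted through the confidence interval and will not be read as evidence of no effect.

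Add free estradiol to the endpoints in Section 8.0 and to the mixed-model outcomes in Section 11.0.

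The cost is a text edit and a less favourable stated power. No participants, visits or assays are added.
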